8.2. Justification of key secondary and exploratory outcomes

8.2.1. Headache

Headache is the primary presenting symptom in IIH². The condition causes significant morbidity, with headaches being a major contributor to reduced QoL^{12,13}. Headache in active IIH is closely linked to elevated ICP, with improvements in severity and frequency observed following CSF removal, shunt placement, or weight loss⁶⁰⁻⁶². Studies show a significant correlation between changes in ICP and headache severity or frequency¹⁴. The IIH Weight Trial indicated that reducing ICP through weight management led to improvements in headache outcomes²⁵.

The American Headache Society and International Headache Society recommend using headache outcomes derived from a 28-day diagnostic diary to assess treatment. This diary tracks headache frequency, severity and acute analgesic medication use.

8.2.2. Monthly headache days

Monthly headache days (MHD) will include all headache days, defined as those with an onset, continuation or recurrence of any severity or phenotype of headache and lasting at least 30 minutes or which require acute headache analgesia in a month (28 days).

8.2.3. Monthly migraine days

Monthly migraine days indicate the mean number of days a month (28 days) where a migraine or probable migraine is present. Migraine is diagnosed by the International Classification of Headache Disorders 3rd edition beta⁶³. In IIH, headaches are migraine-like but cannot fulfil the full criteria for migraine as a secondary cause is present. However, for the purposes of classification in this trial we will use the International Classification of Headache Disorders definitions for migraine and probable migraine.

8.2.4. Headache responder rate

Headache responder rate ($\geq 50\%$ reduction in MHD from baseline) is the proportion of participants achieving at least 50% reduction in the number of MHD. This is clinically relevant as it is used as an empirical review for continuing or discontinuing headache therapy⁶⁴. As a sensitivity analysis, we will appraise the proportion of participants achieving at least a 30% reduction in the number of MHD.

8.2.5. Headache severity

Some treatments may not reduce MHD, but can improve severity, leading to functional benefits and reduced disability, which is clinically relevant⁶⁵. Headache severity is assessed by an 11-point Numeric Rating Scale (0 = no pain and 10 = most severe pain). The monthly headache severity is calculated as the mean severity with the denominator as the number of MHD.

8.2.6. Monthly use of acute headache rescue medications

Up to 48% of IIH patients experience medication overuse headaches and this can exacerbate the headache burden⁶⁶. Acute headache analgesic use reflects treatment inefficacy and is a helpful secondary outcome. Reduction in analgesic days is linked to IIH clinical remission²⁶. We will measure the number of days per month that acute headache analgesic medication is used.

8.2.7. Headache disability

The Headache Impact Test-6 (HIT-6) is a 6-item self-report tool used to assess the disability and impact of headaches on daily life, including areas such as work, social activities, and relationships. Responses are rated on a 5-point scale, with higher scores indicating greater impact. The total score categorises the severity of headache-related disability as mild, moderate, or severe.

8.2.8. Absenteeism and presenteeism

The Work Productivity and Activity Impairment (WPAI) Scale is a widely used, validated tool for assessing the impact of health conditions on work productivity and daily activities⁶⁷. It measures both absenteeism (time missed from work) and presenteeism (reduced productivity while at work), as well as overall activity impairment. It is widely used in headache studies to understand the significant impact of headaches on work productivity and daily activities^{68,69}.

8.2.9. Quality of life in IIH

IIH negatively affects quality of life; primarily driven by headaches^{12,13,24}. Measures of vision (the visual field) correlate with quality of life⁷⁰. While there is no IIH-specific quality of life measure, most trials in IIH use the 36-item Short Form (SF-36) health survey, which correlates with changes in ICP^{13,14,17,19,70}. The EQ-5D-5L is used for cost-effectiveness assessments lacks sensitivity compared to the SF-36 for IIH^{19,71}. The National Eye Institute Visual Function Questionnaire-25 and 10-item supplement assesses visual-related quality of life and is linked to visual field improvements^{70,72,73}, with the 10-item neuro-ophthalmic supplement discriminating in a prior IIH trial¹⁷.

8.2.10. Binge eating

Binge eating can influence weight gain. Approximately 7.5–30% of obese individuals seeking treatment have binge eating disorder or subclinical binge eating⁷⁴. The validated Binge Eating Scale (BES) can be used to identify binge eaters^{75,76}, and has proven effective for both diagnosis and treatment monitoring⁷⁵. Individuals with BES scores <18 are classified as non-binge eaters.

8.2.11. Alcohol use disorders identification test

The Alcohol Use Disorders Identification Test (AUDIT) is a tool developed by the WHO to identify individuals at risk for alcohol use disorders. It consists of 10 questions that assess alcohol consumption, drinking behaviours, and alcohol-related problems. The scoring ranges from 0 to 40, with a score of 8 or more suggesting hazardous or harmful drinking.

8.2.12. Hospital Anxiety and Depression Scale

IIH can significantly impact mental health leading to depression (42%) and anxiety (47%)⁷⁷. The Hospital Anxiety and Depression Scale (HADS) is a widely used self-report questionnaire designed to assess levels of anxiety and depression in non-psychiatric hospital patients. The items are scored on a 4-point scale, yielding scores for both subscales, with higher scores indicating greater severity of symptoms. The HADS is

valued for its simplicity, ease of administration, and ability to distinguish between anxiety and depression, making it a useful tool in clinical and research settings, particularly in medical populations where somatic symptoms may overlap with psychological distress.

8.2.13. Exploratory sleep outcomes

Obesity significantly alters sleep patterns, increasing the risk of sleep disturbances such as obstructive sleep apnoea (OSA). Sleep has not been studied in IIH, but OSA is a known complication in IIH⁷⁸. GLP-1R agonists have been shown to reduce weight and so improve OSA⁷⁹. Additionally, GLP-1R agonists have also been shown to increase non-rapid eye movement sleep in rodents which may contribute to the overall positive effects on health which can be observed in these drugs⁸⁰. We will evaluate the effects of weight loss driven by GLP-1R agonist Tirzepatide on sleep and how this might impact headache and mental health outcomes.

9. Trial procedures

9.1. Screening assessment (Month -1)

Following consent, participant contact details including telephone number will be collected. Email address will be collected during the consent process.

Participants will then be asked to provide a letter from an NHS medical professional confirming a diagnosis of IIH (correspondence may be available on the participant's NHS app). This will be reviewed by the research medical team to confirm a diagnosis of IIH. Where the correspondence is unclear, further documentation may be requested. Confirmation from a private health care provider will be considered on a case-by-case basis by the CI.

The participant will be asked to provide their height and weight. BMI will be calculated by the EDC.

A provisional baseline appointment may be arranged and Trial Office will liaise with Specsavers and the participant to arrange an OCT scan at a participating Specsavers UK store of the participant's choice. The resulting report (comprising solely of TNO and RNFL measurements) will be sent by email to the Trial Office and entered onto the EDC to allow a Trial Researcher to determine participant's level of papilloedema is sufficient to meet the trial eligibility.

If the participant is potentially eligible to continue into the trial on review of the OCT scan, then a baseline appointment will be arranged/confirmed.

Capillary (finger prick) blood, saliva, 24-hour urine and stool collection kits will be posted to the home address of the participant and information will be provided for collection. A video describing how each sample is collected, stored and posted will be shared with the participants and be available on the IIH-Advance website. Electronic scales and a paper tape measure will be provided to participants by post. A wearable device to capture exploratory sleep actigraphy data for 2 weeks will be provided to participants by post, and a link for an accompanying sleep diary, to be completed daily for 2 weeks, will be provided. This link will direct the participant to a subsection of the secure trial-specific EDC. If the participant is female of childbearing potential, the Trial Office will post a urine pregnancy test. This should be completed by the participant up to 7 days before the baseline assessment. The participant will provide the date the urine pregnancy test was completed at the baseline appointment.

It will be attempted to review OCT scans and post sample kits, sleep devices and pregnancy tests more than 2 weeks before baseline wherever possible.

9.2. Baseline visit (Month 0)

The baseline visit will take place via video call and last approximately 60-90 minutes. During this visit, full eligibility for randomisation will be confirmed by the Trial Doctor who will also ask the participant to

verbally confirm that they are happy to continue. Participant medical history, relevant current medications and demographic information including ethnicity and gender will be collected by the researcher.

The baseline 28-day headache diary will be reviewed, so the trial researcher can record the monthly headache days, monthly migraine days, monthly analgesic days and monthly headache severity.

The following validated questionnaires will be completed by the Trial Researcher reading out the questions and recording the participant's answers onto the EDC:

- Headache disability questionnaire (HIT-6)
- SF-36 v2
- EQ5D-5L
- NEI-VFQ-25 with 10 Item Neuro-Ophthalmic Supplement
- Binge eating questionnaire (BES)
- Alcohol intake questionnaire (AUDIT)
- Hospital Anxiety and depression Scale (HADS)
- CSRI
- Work Productivity and Activity Impairment (WPAI) Scale
- Pittsburgh Sleep Quality Index (PSQI)
- Insomnia Severity Index (ISI)
- Berlin questionnaire
- STOP-Bang sleep apnoea screening questionnaire

Once all baseline assessments are complete, the researcher will randomise the participant as per **section 6**.

9.3. Monthly follow up visits (month 1-5, 7-11, and 13-17)

Monthly after randomisation the participant will be invited to attend a video call with a trial researcher to review weight, headache, and intervention compliance. These video calls will last approximately 30-60 minutes and include:

Researcher collection of:

- Weight (as demonstrated during the videocall or by photograph of the provided scales)
- Visual inspection of Tirzepatide pen (if participant randomised to receive Tirzepatide)
- Concomitant medications
- Participant's monthly headache history
- Postage of sample collection kit to participant (prior to months 3 and 6)
- Postage of exploratory sleep wearable device (months 3 and 6)

Participant completion of:

- CSRI
- HIT-6
- Blood, saliva, 24-hour urine and stool samples (sent prior to months 3 and 6)
- Two weeks of exploratory sleep wearable device actigraphy collection, two weeks of daily sleep diary (months 3 and 6)

9.4. Review and treatment allocation visit R2 (month 6)

With sufficient notice before the 6 month time point, an OCT scan will be arranged at a participating Specsavers UK store of the participant's choice, to be completed <2 weeks before the 6 month time point.

Then, at 6 months, a full review as per the baseline visit as detailed in **section 9.2** (minus height, demographics and medical history) will be carried out.

Once the OCT scan has been analysed by the trial researcher and all month 6 assessments have been completed, participants will be classed as responder, partial responder or non-responder.

- Responders to standard of care will leave the trial.
- Non-responders to Tirzepatide will proceed to their final follow up visit (**section 9.6**).
- Responders and partial responders to Tirzepatide, and partial and non-responders to standard of care will be re-randomised into R2 as per the R1 randomisation method in **section 6**.

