3.1.1. Stage R1

In the first stage, R1, 86 people with IIH will be randomised in a 1:1 ratio to either Tirzepatide with standard of care or standard of care alone for 6 months. The primary outcome is resolution of papilloedema, with those participants in whom there is resolution of papilloedema classed as responders and those with partial resolution of papilloedema classified as partial responders for the purposes of re-randomisation.

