3.1.2. Stage R2

[figure not shown]
After 6 months, stage R1 will end and participants will have a 6 month follow up appointment. Their papilloedema will be reviewed and they will be re-randomised and enter stage R2 if they could still potentially benefit from Tirzepatide:

- Participants who have resolution or partial resolution of papilloedema as measured by OCT after 6 months of treatment with Tirzepatide plus standard of care will be randomised again to either Tirzepatide plus standard of care vs standard of care. This will allow evaluation of the maintenance of effect compared to those who discontinue treatment at 12 months. Discontinuing will enable evaluation of the impact of drug cessation on weight change and its impact on IIH at 12 months, compared to those continuing Tirzepatide plus standard of care.
- Participants who have no resolution of papilloedema as measured by OCT after 6 months of treatment with standard of care will be randomised again to either Tirzepatide plus standard of care or standard of care for 6 months. This will allow evaluation of the effect of delayed initiation of weight loss induced by Tirzepatide for 6 months on IIH, again at 12 months, compared to standard of care.

Participants will not be randomised again if they are unlikely to benefit from Tirzepatide:

- Participants who have no resolution of papilloedema after 6 months of Tirzepatide plus standard of care will not be eligible to be re-randomised as their IIH symptoms are unlikely to benefit from a second 6-month course of treatment.
- Participants who have resolution of papilloedema after 6 months of standard of care will not be eligible to be re-randomised as their IIH symptoms would not benefit from weight loss and starting Tirzepatide.

Participants who receive Tirzepatide in stage R2 will leave the trial after this 6 month treatment period.

Figure 3: Trial Schema

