6.3. Second randomisation (R2)

A second stage of randomisation will commence for participants who were:

1. Allocated Tirzepatide in R1 and showed a response or partial response
2. Allocated Standard care in R1 and showed partial or no response

These participants will be randomised 1:1 to receive either Tirzepatide plus standard of care or standard care. This stage will last 6 months as per **section 3.1.2**.

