6.6. Blinding

IIH-Advance is an unblinded trial. It is not possible to perform a blinded controlled trial of Tirzepatide due to the extent of weight loss expected⁴² even if a placebo injection was introduced as a control arm. The primary outcome will be based on the objective measurement of RNFL by OCT as output by the OCT machine operated by Specsavers' staff blinded to a participant's allocation.

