8.1. Main trial outcomes

8.1.1. Primary outcome

Resolution of papilloedema, as measured by OCT at 6 months post-randomisation.

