16.1. Sample size

Examination of various IIH datasets held (including the IIH:WT trial²⁵, the IIH:Life cohort, and our previously published clinical trials in IIH²⁶) suggest it is anticipated that in the population of patients who receive standard of care only 5% will have resolution of papilloedema (100% reduction in the excess elevation of the optic nerve swelling). Further analysis of these datasets revealed that in those who achieved at least a 12% reduction in body weight, between 30 and 50% had a complete resolution of papilloedema. For the purposes of the sample size calculation, we have taken a conservative estimate of 37% (the median estimate).

With a type I error of 0.05, a type II error of 0.1 (corresponding to a power of 90%), a responder rate in the control arm of 5% and responder rate of 37% in the Tirzepatide arm, a sample size of 32 participants per arm is required. Inflating this to account for 25% attrition (for missing data and withdrawal) would require 43 patients per arm (86 overall).

After 50% of the planned sample size has been recruited and treated (i.e. at the end of the first randomisation R1), an assessment of the missing data is planned to ensure the levels observed fall below that assumed during this calculation, with the option to increase the sample size based on this if needed. This trial has been powered to answer the primary question for R1 only. The subsequent questions remain unpowered. This remains a limitation, however powering for these questions would result in a trial sample size that was infeasible. The purpose of these questions is to provide some high-quality evidence.

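### Section 9.4 places a researcher who is not blinded between the blinded RNFL measurement and the month-6 response class, and in the standard-of-care arm the responder boundary sets both the primary outcome and exit from the trial

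*Protocol*

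**What the plan says.** The primary outcome (Protocol 8.1.1) is binary: "Resolution of papilloedema, as measured by OCT at 6 months post-randomisation". Its only stated meaning is in 16.1, where resolution is a "100% reduction in the excess elevation of the optic nerve swelling". Section 3.1.1 links it to the classes used for re-randomisation, with "those participants in whom there is resolution of papilloedema classed as responders and those with partial resolution of papilloedema classified as partial responders".

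On blinding, 6.6 says the trial is unblinded and relies on the measurement: "The primary outcome will be based on the objective measurement of RNFL by OCT as output by the OCT machine operated by" Specsavers staff who do not know the allocation. Under 5.5 and 9.1 (for screening) and section 21 (generally), the trial team receives only the trial number and the OCT or RNFL measurements.

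At month 6, section 9.4 says: "Once the OCT scan has been analysed by the trial researcher and all month 6 assessments have been completed, participants will be classed" into three groups. Standard-of-care responders leave. Standard-of-care partial responders and non-responders are re-randomised. Tirzepatide responders and partial responders are re-randomised, and Tirzepatide non-responders go to final follow-up.

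On R2 entry for the control arm, 3.1.2 says: "Participants who have no resolution of papilloedema as measured by OCT after 6 months of treatment with standard of care will be randomised again". Section 6.3 lists those "Allocated Standard care in R1 and showed partial or no response".

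On location, 9.4 says "an OCT scan will be arranged at a participating Specsavers UK store" that the participant chooses. Section 6.5 has a nominated store notified at randomisation and Specsavers asked to book the scan due six months later.

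**The concern.** The blinding safeguard ends one step early. The machine output is protected, but the step from RNFL values to a response class is not. Trial researchers inspect used pens (7.5) and review weight and medication every month (9.3), and no separate blinded reader is provided for.

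The consequences of the class differ by arm. A standard-of-care responder leaves, and section 24 offers no Tirzepatide after the trial. A standard-of-care partial responder is re-randomised and, if allocated standard of care again, is offered Tirzepatide in SA3 (3.1.3, 6.4). Whoever analyses the scan can know this. A borderline control participant moved down one class keeps a route to the drug and also counts as a failure on the primary outcome. No matching pull exists in the Tirzepatide arm, where access turns on partial responder versus non-responder and both are failures on the primary outcome. Any leaning would therefore favour Tirzepatide on the only powered endpoint.

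**Working it through.** **1. What each boundary decides (3.1.1, 9.4).**

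| Arm | Boundary | Changes primary outcome? | Changes R2 entry? |
|---|---|---|---|
| Standard of care | responder / partial | yes | yes |
| Standard of care | partial / non-responder | no | no (both enter R2 under 6.3 and 9.4) |
| Tirzepatide | responder / partial | yes | no (both enter R2) |
| Tirzepatide | partial / non-responder | no | yes |

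Only the first row does both.

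**2. The plan's own figure.** Inputs from 16.1: rates 0.05 and 0.37, type I error 0.05 (taken as two-sided), power 90%. The mean rate is 0.21.

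n = [1.960·√(2·0.21·0.79) + 1.282·√(0.05·0.95 + 0.37·0.63)]² / 0.32² = (1.129 + 0.679)² / 0.1024 ≈ 31.9, so 32 per arm. Then 32/0.75 = 42.7, so 43 per arm and 86 overall. The stated size reproduces, and nothing here disputes it.

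**3. Size at the planned rates.** The protocol gives no misclassification rate, so let m be an assumed share of true control responders classed below responder. The observed control rate is 0.05(1 − m).

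| m | Control rate | Risk difference (points) | Risk ratio |
|---|---|---|---|
| 0 | 5.0% | 32.0 | 7.4 |
| 10% | 4.5% | 32.5 | 8.2 |
| 25% | 3.75% | 33.25 | 9.9 |
| 50% | 2.5% | 34.5 | 14.8 |

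In counts: 43 × 0.05 = 2.15 and 43 × 0.37 = 15.91, or about 2 and 16. With 16/43 against 2/43 the difference is 14/43 = 32.6 points and the ratio 8. With 16/43 against 1/43 they are 15/43 = 34.9 points and 16. These counts assume that everyone is scanned. With 32 of 43 evaluable and missing counted as failure (16.2.1), about 32 × 0.05 = 1.6 control responders are expected.

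**4. False-positive rate if the treatment had no effect.** This is an exact binomial enumeration of the two-sided Pearson test at 43 per arm, with equal true rates and share m of control responders downgraded.

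| True rate in both arms | m = 0 | 10% | 25% | 50% |
|---|---|---|---|---|
| 5% | 4.7% | 4.6% | 4.9% | 6.6% |
| 20% | 5.3% | 6.0% | 9.7% | 26.4% |
| 37% | 5.5% | 7.0% | 15.6% | 49.4% |

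At the planned control rate the inflation is slight. It becomes material only if control resolution is far more common than assumed.

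**5. Where standard-of-care partial responders fall.** In 3.1.2, *no resolution* on Tirzepatide must exclude partial resolution, because partial resolvers in that arm are re-randomised. On standard of care the same words must include partial resolution in order to agree with 6.3 and 9.4. Otherwise 3.1.2 does not say where those participants go. By the table in step 1 this does not touch the primary outcome.

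**6. Store and device.** Section 9.4 leaves the store to the participant, 6.5 refers to a nominated store, and no section requires the same device. For illustration, suppose a device change caused equal false-positive and false-negative rates e in all participants, so that each rate p becomes p(1 − e) + (1 − p)e. Power at 32 per arm would be 90.1% at e = 0, 85.9% at 2%, 78.5% at 5% and 64.3% at 10%. The values of e are assumptions, and only participants who changed device would be affected.

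**The case against.** The strongest reply is that little discretion exists. The researcher receives numbers, not an image to grade. Resolution has one stated meaning, and cut-offs and an eye rule may properly sit in the SAP or working instructions. Section 9.4 names the researcher as analysing the scan but does not name who classes the participant. The other month-6 assessments must precede the classing, but not necessarily the scan analysis. The only documented stake is the participant's, and the participant cannot alter machine output. All of this stands, and the absence of cut-offs is not the complaint. What remains is that the protocol itself assigns the analysis to an unblinded role, and that the class is acted on at month 6, when control responders leave. A rule applied only at the final analysis would come too late for that decision.

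Four stronger readings are tempting, and the protocol does not support them:

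- A reader might infer that the three-level class is the primary outcome. It is not. Only resolved versus not resolved is (8.1.1, 16.2.1), and nothing says that the analysis must use the month-6 label.
- A reader might infer that the double use of *no resolution* threatens the powered comparison. It concerns entry to R2, whose questions are exploratory and unpowered (2.1.3, 16.1).
- A reader might infer that scanners will change and thereby bias the result towards Tirzepatide. A change is only permitted, 6.5 points towards one nominated store, and device error of that kind would not be directional.
- A reader might take the risk ratio rising from 8 to 16 as the size of the problem. It reflects one of about two expected events, while the risk difference moves by 1/43, or 2.3 points.

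**Conclusion.** The point holds as a gap in the safeguard, not as a demonstrated bias. Blinding covers the measurement but not the step to the response class. At one boundary, responder versus partial responder under standard of care, that step decides both the primary outcome and whether the participant leaves. Any leaning there would favour Tirzepatide. The size is unknown because no misclassification rate is given. At the planned 5% versus 37% the risk difference would move by about 1 to 2.5 points for assumed downgrading of 25% to 50%. The false-positive rate would be affected materially only if true control resolution were nearer 20% or more. The conclusion assumes that the analysing researcher is not shielded from the allocation, which follows from 6.6 and 7.5, and that some latitude exists between RNFL values and class. The conflicts over *no resolution* and over the store are real but secondary.

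**What to change.** - **Section 9.4:** have the EDC derive the class from the RNFL values sent by Specsavers, under a rule (including how two eyes are combined) locked before the first month-6 scan, with no researcher override. Use that same derived variable for the primary analysis and for R2 entry.
- **Sections 3.1.2, 6.3 and 9.4:** use the three class names consistently and reconcile where standard-of-care partial responders fall. Which entry rule applies is for the sponsor to decide.
- **Sections 6.5 and 9.4:** reconcile the nominated store with the participant's choice by booking follow-up scans at the baseline store and device by default, and record the device at every scan.

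The cost is one EDC derivation, a few wording changes, and slightly less choice of store, chiefly for participants who move. Travel to scans is already reimbursed up to £20 per visit (19.6).
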